Appendix J
Minnesota Tobacco Withdrawal Scale

How are you feeling at this very moment? Please mark an (X) in ONE box for each condition					
	Not at all	Slightly	Somewhat	Very	Extremely
Depressed					
Irritable					
Anxious, nervous					
Restless					
Dizziness					
Hungry					
Nausea					
Poor concentration					

Appendix K
The Positive Negative Affect Scale (PANAS)

This scale consists of a number of words that describe different feelings and emotions. Read each item and then mark the appropriate answer in the space next to that word. Indicate to what extent you feel this way right now, that is, at the present moment. Remember, there is no right or wrong answer so please give us your honest opinion.

1 very slightly or not at all	2 a little	3 moderately	4 quite a bit	5 extremely
-------------------------------------	---------------	-----------------	------------------	----------------

_____ interested	_____ Irritable
_____ Distressed	_____ Alert
_____ Excited	_____ Ashamed
_____ Upset	_____ Inspired
_____ Strong	_____ Nervous
_____ Guilty	_____ Determined
_____ Scared	_____ Attentive
_____ Hostile	_____ Jittery
_____ Enthusiastic	_____ Active
_____ Proud	_____ Afraid

Appendix L

Product Evaluation Form: Satisfaction With and Helpfulness of the Product

Please answer the following questions about the Nicotine Solution you just used. Please mark an (X) in ONE box for each question					
	Much less than my regular device & e-liquid	A little less than my regular device & e-liquid	The same as my regular device & e-liquid	A little more than my regular device & e-liquid	Much more than my regular device & e-liquid
1. How good did it taste?					
2. How pleasant was it?					
3. How much did it relieve your urge to vape					
4. How was the effect of the e-Cig vapor on your:					
Tongue?					
Nose?					
Back of mouth and throat?					
Windpipe?					
Chest?					
5. How harsh was it?					
6. How much e-cigarette taste					

versus 'just air' did you get?					
	Much less than my regular device & e-liquid	A little less than my regular device & e-liquid	The same as my regular device & e-liquid	A little more than my regular device & e-liquid	Much more than my regular device & e-liquid
7. Was it embarrassing to use in front of others?					
8. How hard was it to draw vapor from?					
9. How fast did it relieve your urge to vape?	It did not relieve my urge to smoke 	Within a few puffs 	Within 5 minutes 	Within 10 minutes 	Within 15 minutes 

10.) How satisfying did you find the ENDS product and solution compared to your normal

11.) How enjoyable did you find the ENDS product and solution compared to your regular device and solution? (please mark an (X) on ONE of the boxes)

1	2	3	4	5	6	7	8	9	10
									→
cigarettes									

Not enjoyable at all → *As enjoyable as normal cigarettes*

12.) How dangerous to your health did you find the ENDS product and solution compared to your regular device and solution? (please mark an (X) on ONE of the boxes)

[figure not shown]
1	2	3	4	5	6	7	8	9	10
---	---	---	---	---	---	---	---	---	----

Less dangerous than normal cigarettes → *More dangerous than normal cigarettes*

[figure not shown]

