1 OBJECTIVES

- To determine the effect of nicotine salt (nicotine benzoate) and free-base nicotine in different flavored e-liquid solutions on puffing behaviors and systemic exposure to nicotine from ENDS by 1) Assessing short-term effects on nicotine cravings, withdrawal, and satisfaction from single use of ENDS refilled with flavored nicotine salt or flavored free-base nicotine solutions with two different flavors (tobacco or unflavored) in current daily ENDS users following an overnight fast; and 2) Comparing users' perceptions and preferences towards inhaling vapors containing nicotine salt (nicotine benzoate) or free-base nicotine with two different flavors (tobacco and unflavored) versus their regular brand.
- This project provides important information on whether the pharmacokinetics of nicotine delivery differ between salt and free-base forms of e-liquid of equivalent nominal concentration using the same device, and whether the previously observed effects of flavors on subjective effects differ between salt and free-base forms.

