3.2 Exclusion Criteria

- Smoked cigarettes in the past 7 days.
- Currently smokes \geq 5 cigarettes per month.
- Unstable medical conditions (such as unstable heart disease, uncontrolled hypertension, thyroid disease, diabetes, renal or liver impairment, or glaucoma) or psychiatric condition (such as current major depression, history of schizophrenia or bipolar disorder) or current regular use of psychiatric medications (such as major tranquilizers and antidepressants).
- History of serious side effects from nicotine or from any nicotine replacement therapies.
- Uncontrolled intercurrent illness including, but not limited to, ongoing or active infection, symptomatic congestive heart failure, unstable angina pectoris, cardiac arrhythmia, or psychiatric illness/social situations that would limit compliance with study requirements.
- Pregnant or nursing females.
- Concurrent participation in another clinical trial

Roswell Park Protocol No.: I 475819

- Unwilling or unable to follow protocol requirements.
- Any condition which in the Investigator's opinion deems the participant an unsuitable candidate.

Refer to **Appendix B** for the Investigator Study Eligibility Verification Form: Inclusion Criteria.

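### Appendix L, items 11 and 12: the question compares with the regular device but the scale ends name cigarettes, so these two scores have no defined comparator

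*Combined protocol and SAP*

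**What the plan says.** Section 1 sets out to compare users' perceptions and preferences for the salt and free-base liquids "with two different flavors (tobacco and unflavored) versus their regular brand". Section 11 and Table 3 schedule Appendix L after product use at all four visits, and Section 11 describes it as an adapted questionnaire.

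Within Appendix L:

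- Items 1 to 8 use a five-column grid running from much less to much more than the participant's regular device and e-liquid, with equality in the middle.
- Item 9 asks how fast the urge to vape was relieved, but its first answer is "It did not relieve my urge to smoke".
- Item 11 asks "How enjoyable did you find the ENDS product and solution compared to your regular device and solution". Its 1 to 10 scale runs from no enjoyment at all to "As enjoyable as normal cigarettes".
- Item 12 asks "How dangerous to your health did you find the ENDS product and solution compared to your regular device and solution". Its 1 to 10 scale runs from less dangerous than normal cigarettes to "More dangerous than normal cigarettes".

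Section 3.2 excludes anyone who "Smoked cigarettes in the past 7 days". No criterion in Section 3.1 requires a smoking history. Appendix F allows a participant to report never having smoked, and Appendix R offers an answer for people who never smoked regularly.

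**The concern.** In items 11 and 12 the stem and the printed ends name different comparators. The participants are daily vapers who have not smoked for at least a week, and some may never have smoked regularly. For them cigarettes may be a distant or unknown reference. Two people with the same opinion of a liquid can therefore mark different boxes, depending on which part of the item they follow.

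This matters most for the regular-brand aim in Section 1, because that comparison reads the level of the score itself. Appendix O ranks only the four test solutions against each other. The two own-brand questions in Appendix Q ask about similarity, not better or worse. Items 11 and 12 are the only Appendix L items on enjoyment and on perceived danger relative to the participant's own product. Answers given under an unclear comparator cannot be reinterpreted afterwards.

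**Working it through.** The plan states no figure on this point, so the check is a comparison of texts.

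**Step 1: classify the 12 numbered items of Appendix L.**

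| Items | Comparator in stem or grid | Comparator in scale ends | Status |
|---|---|---|---|
| 1–8 | regular device and e-liquid | regular device and e-liquid | consistent, with midpoint |
| 9 | none (time to relief) | none | wording slip, smoke for vape |
| 10 | text cut off | not readable | cannot be judged |
| 11 | regular device and solution | normal cigarettes (upper end) | conflict, no room above equality |
| 12 | regular device and solution | normal cigarettes (both ends) | conflict |

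Count: 8 + 1 + 1 + 2 = 12. The conflict is shown in 2 of 12 items.

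**Step 2: is it a text-extraction fault?** The layout around item 10 is broken. The labels in question carry the words for enjoyment and danger, however, which tie each to its own item. The conflict in items 11 and 12 is in the form itself.

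**Step 3: what each reading does to the score.** Take a participant who finds a liquid exactly equal to their own device.

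- Item 12 read by the stem: the answer is the middle, (1 + 10)/2 = 5.5, which falls between boxes 5 and 6.
- Item 12 read by the labels: the answer is wherever the participant places their own device relative to cigarettes.
- Item 11 read by the stem: equality is the top box, 10. A liquid that is better than the comparator also scores 10.
- Item 11 read by the labels: the answer again depends on own device versus cigarettes, with the same ceiling.

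**Step 4: where the confusion cancels and where it does not.** Suppose, as a simplification, that a participant i who follows the labels gives liquid j the score b_ij + c_i. Here b_ij is the liquid versus the own device and c_i is the own device versus cigarettes.

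- Level, needed for the regular-brand aim: mean score = mean(b) + mean(c). Appendix L does not measure c, so b cannot be recovered.
- Difference between two test liquids: (b_ij + c_i) − (b_ik + c_i) = b_ij − b_ik. The unwanted part drops out, which is the role of the random subject effect in Section 19.5.

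The second result fails if a participant switches between stem and label across visits, which adds noise. It also fails if liquids reach the ceiling of item 11, which compresses differences.

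**Step 5: does a planned analysis rest on these items?** The primary endpoints in Section 8.1 are pharmacokinetic. The secondary endpoints in Section 8.2 are harshness, satisfaction, liking and withdrawal relief; perceived danger is not among them. Harshness is item 5, which is correctly anchored. Liking is also asked in Appendix M (item 4) and in the Duke items of Appendix Q, satisfaction in Appendix Q, and withdrawal in Appendix J. The secondary test is the base-by-flavor interaction. Section 19 contains no regular-brand contrast.

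**The case against.** The strongest reply is that this is a two-item wording fault on a form that otherwise works. Items 1 to 8 already provide a balanced scale against the regular device, covering taste, pleasantness, relief of urge, sensory effects, harshness, taste versus air, embarrassment and draw. Appendix Q adds own-brand similarity. No endpoint or model names items 11 or 12, and a stable personal reading of the scale largely drops out of comparisons between test liquids.

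All of this stands, and it sets the limits of the point. A reader might infer that Appendix L as a whole cannot answer the regular-brand comparison; items 1 to 8 show otherwise. A reader might also infer that item 10 has the same fault. Its stem is cut off and its scale is missing in the available text, so it can only be checked, not cited. Item 9 has no comparator, and its slip is one of wording.

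The reply does not remove the conflict in items 11 and 12 or the ceiling in item 11. Nor does the plan say which questionnaire items supply the satisfaction and liking endpoints, so use of item 11 for one of them is not ruled out.

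**Conclusion.** The point holds for items 11 and 12 only. These two scores cannot be read as a comparison with the regular brand, and item 11 cannot record a liquid preferred to its comparator. The regular-brand aim remains answerable on the subjects that items 1 to 8 cover.

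A reader might go further and infer that the planned secondary tests are compromised. The documents do not support that: the tests contrast the test liquids with each other, and other items measure each secondary endpoint. The primary pharmacokinetic analysis is untouched.

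The size is 2 of 12 items. A shift in scale points cannot be derived, because the documents hold no data on how participants rate their own device against cigarettes. The cancellation in liquid-versus-liquid contrasts assumes that each participant reads the scale the same way at every visit and that item 11 does not reach its ceiling. The correction is worth making because the form is used at every visit and the change is nearly free.

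**What to change.** - Relabel both ends of items 11 and 12 against the regular device and solution, with a midpoint meaning the same as the regular device and solution. Ten boxes have no central box, so either label the point between 5 and 6 or move both items into the five-column grid of items 1 to 8.
- In the first answer of item 9, replace smoke with vape.
- Check the stem and scale of item 10 in the original form, and correct them only if they show the same conflict.
- If answers already exist, flag items 11 and 12 collected on the old form and leave them out of any regular-brand claim. Where possible, start the new form at a participant's first visit, so that all four visits of one person use the same scale.

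The cost is a text edit to the form and to REDCap with notice to the IRB, plus the loss of any earlier answers to these two items for the regular-brand comparison. Visits, sample size and planned models do not change.

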Appendix M –Drug Effect Questionnaire

This questionnaire asks about how you are feeling after using the provided nicotine product. Please draw a mark on the line to show how strongly you are feeling each of the following effects right now. You can mark anywhere on the line, but please draw a vertical line (one that goes straight up and down).

[figure not shown]
1. Do you FEEL a nicotine effect right now?

NOT AT ALL EXTREMELY

[figure not shown]
2. Are you HIGH right now?

NOT AT ALL EXTREMELY

[figure not shown]
3. Do you DISLIKE any of the effects you are feeling right now?

NOT AT ALL EXTREMELY

4. Do you LIKE any of the effects you are feeling right now?

NOT AT ALL EXTREMELY

5. Would you like MORE nicotine right now?

NOT AT ALL EXTREMELY

Appendix N

Modified Questionnaire of Smoking Urges (QSU-breif)

Please answer each statement below on a scale from 0 (Strongly Disagree) to 100 (Strongly Agree)

1. I have a desire for my regular device and e-liquid right now. _____
2. Nothing would be better than using my regular device and e-liquid right now. _____
3. If it were possible, I would probably use my regular device and e-liquid right now. _____
4. I could control things better right now if I could use my regular device and e-liquid right now. _____
5. All I want right now is my regular device and e-liquid right now. _____
6. I have an urge for my regular device and e-liquid right now. _____
7. My regular device and e-liquid would taste good right now. _____
8. I would do almost anything for my regular device and e-liquid right now. _____
9. Using my regular device and e-liquid would make me less depressed. _____
10. I am going to use my regular device and e-liquid as soon as possible. _____

Appendix O
Nicotine Solution Rating Scale

1.) Please order the following nicotine solutions you tested from 1- 4 based on how satisfied you were with the solutions.

(4= Most satisfying and 1= Least satisfying)

Product	Rating
Solution A	_____
Solution B	_____
Solution C	_____
Solution D	_____

Appendix P

Experimental Tobacco Marketplace

[figure not shown]
Account Balance	\$50.00	Cart Total	\$0.00

 
 
  
\$16.79
 
JUUL E-Cigarette Classic Tobacco 160 mg nicotine/91 cigarettes
 
0 
 
Product Description
 
WARNING: This product contains nicotine. Nicotine is an addictive chemical.
 
 
  
\$16.79
 
JUUL E-Cigarette Crème Brûlée 160 mg nicotine/91 cigarettes
 
0 
 
Product Description
 
WARNING: This product contains nicotine. Nicotine is an addictive chemical.
 
 
  
\$16.79
 
JUUL E-Cigarette Fruit Medley 160 mg nicotine/91 cigarettes
 
0 
 
Product Description
 
WARNING: This product contains nicotine. Nicotine is an addictive chemical.
 
 
  
\$16.79
 
JUUL E-Cigarette Mango 160 mg nicotine/91 cigarettes
 
0 
 
Product Description
 
WARNING: This product contains nicotine. Nicotine is an addictive chemical.
 
 
  
\$16.79
 
JUUL E-Cigarette Menthol 160 mg nicotine/91 cigarettes
 
0 
 
Product Description
 
WARNING: This product contains nicotine. Nicotine is an addictive chemical.
 
 
 
			

 
 
  
\$16.79
 
JUUL E-Cigarette Virginia Tobacco 160 mg nicotine/91 cigarettes
 
0 
 
Product Description
 
WARNING: This product contains nicotine. Nicotine is an addictive chemical.
 
 
  
\$31.24
 
NicoDerm CQ Patch Clear 147 mg nicotine/84 cigarettes
 
0 
 
Product Description
 
 
  
\$13.65
 
Nicorette Gum Cinnamon Surge 80 mg nicotine/46 cigarettes
 
0 
 
Product Description
 
 
  
\$13.65
 
Nicorette Gum White Ice Mint 80 mg nicotine/46 cigarettes
 
0 
 
Product Description
 
 
  
\$18.99
 
Nicorette Lozenge Mint 80 mg nicotine/46 cigarettes
 
0 
 
Product Description
 
 
 
			

Appendix Q

[figure not shown]
Sensory Measures

Based on the e-liquid you just tried, please rate the taste on the following characteristics:

[figure not shown]
1.) Pleasantness

[figure not shown]
2.) Irritation

[figure not shown]
3.) Relaxing

[figure not shown]
4.) Satisfying

[figure not shown]
5.) Sweet

[figure not shown]
6.) Sour

[figure not shown]
7.) Bitter

8.) Cool/cooling

9.) Sharp/biting/astringent/pungent

Sensory		1 Strongly Agree	2	3	4	5	6	7 Strongly Disagree
		E-cigarette Experience Scale						
	1. I like the smell of the vapor.							
	2. I like the taste of vaping.							
	3. I like the feeling of creating vapor clouds.							
	4. I like how creating vapor clouds looks visually appealing / cool.							
	5. I like the flavor of vapor.							
	6. I like how vaping makes me feel good physically.							
	7. I like the feeling of satisfaction that I get from vaping.							
	8. I like the feeling of pleasure that I get from vaping.							
	9. I like doing vape tricks (eg. Blowing vapor clouds or shapes like rings).							

PROMIS-E

	0 Never	1	2	3	4 Almost Always
1. I find myself reaching for my e-cigarette without thinking about it.					
2. I drop everything to go out and buy e-cigarettes or e-juice.					
3. I vape more before going into a situation where vaping is not allowed.					
4. When I haven't been able to vape for a few hours, the craving gets intolerable.					

SHERI-E

Vaping/using an e-cigarette/JUULing is something.....

[figure not shown]
	1 Agree	2	3	4	5	6	7 Disagree
1. I do automatically.							
2. I do without having to consciously remember.							
3. I do without thinking.							
4. I start doing before I realize I'm doing it.							
5. I would find hard not to do.							
6. That is typically "me".							

Duke Sensory Evaluation

Please rate the puffs you just took.

	1 Not at all	2 Very little	3 A little	4 Moderately	5 A lot	6 Quite a lot	7 Extremely
1. How much did you like the puffs you just took?							
2. How satisfying were the puffs you just took?							
3. How high in nicotine do you think the puffs were?							
4. How similar to your own brand were the puffs?							

Rate how strong the puffs were in the following places.

[figure not shown]
5. Strength of puffs on tongue?							
6. Strength of puffs in nose?							

7. Strength of puffs in back of mouth and throat?							
8. Strength of puffs in windpipe?							
9. Strength of puffs in chest?							

[figure not shown]
HEDONIC ATTRIBUTE PROFILE

For each item, please indicate how you would describe the ECIG you just used by placing a mark on the vertical numbered line.

[figure not shown]
1.) Draw

[figure not shown]
2.) Mouthful of vapor

[figure not shown]
3.) Visible vapor

[figure not shown]
4.) Smell

[figure not shown]
5.) Impact

[figure not shown]
6.) Irritation

[figure not shown]
7.) Strength

[figure not shown]
8.) Smoothness

[figure not shown]
9.) Taste

[figure not shown]
10.) Aftertaste

[figure not shown]
11.) Throat hit

[figure not shown]
12.) Dryness

[figure not shown]
13.) Tingling

[figure not shown]
14.) Burning

[figure not shown]
15.) Similarity to usual brand

[figure not shown]
16.) How would you describe the overall flavor sensation of the ECIG you just used?

17.) How would you describe the overall harshness/irritancy of the ECIG you just used?

18.) How would you describe the throat hit of the ECIG you just used?

Appendix R
ENDS Nicotine Dependence Scale

1. If you currently or did you previously smoke cigarettes regularly, how many cigarettes a day do/did you smoke?

- I never smoked cigarettes regularly <0>
- 1 – 10 < 1 >
- 11 – 20 < 2 >
- 21 – 30 < 3 >
- 31+ < 4 >

2. Do you use other forms of tobacco such as cigars, cigarillos, hookah, or smokeless tobacco?

- No < 0 >
- Yes < 1 >

3. Do you vape more frequently during the first few hours after awakening than during the rest of the day?

- Yes < 1 >
- No < 0 >

4. How soon after you wake up do you vape?

- 0 – 5 m < 3 >
- 6 – 30 m < 2 >
- 31 – 60 m < 1 >
- 61+ m < 0 >

5. Of all the times that you vape, which time would you hate most to give up?

- 1st of Day < 1 >
- All Others < 0 >

6. Do you find it difficult to refrain from vaping in places where it is forbidden?

- Yes < 1 >
- No < 0 >

7. How many pods, cartridges, or refills do you typically use each week?

- Less than 1 per week < 0 >
- 1 – 4 per week < 1 >
- 5 or more per week < 2 >

8. How often do you vape?

- 1 day or less each week < 0 >
- 2 – 3 days each week < 1 >
- 4 – 6 days each week < 2 >
- 7 days each week < 3 >
